7.5 Statistical Analyses for Safety

The safety analyses will be performed using the safety population (i.e., Safety Analysis Set). The safety parameters will include AEs, vital sign measurements, 12-lead ECG, laboratory evaluations (hematology and chemistry), neurological assessment (examination to consist of assessment of cranial nerves II through VII), physical examination, and immunogenicity. The last nonmissing safety assessment before study drug administration will be used as the baseline for all analyses of that endpoint.

Treatment-emergent AEs are defined as any AE with the onset that is after the first dose of study drug. Events where the onset date is the same as the study drug start date are assumed to be treatment-emergent, unless known to have started prior to study treatment administration.

An overview of AEs will be presented consisting of the number and percentage of subjects experiencing at least one event for each of the following AE categories:

- 1. Any TEAE
- 2. Any TEAE related to study treatment according to the investigator (i.e., study drug-related, study injection procedure-related)
- 3. Any severe TEAE
 - a. Any severe TEAE related to study treatment according to the investigator
- 4. Any serious TEAE
 - a. Any serious TEAE related to study treatment according to the investigator
- 5. Any TEAE leading to discontinuation of study drug
- 6. Any TEAE leading to death
- 7. PDSOT TEAEs
- 8. Neurological assessment TEAEs
- 9. All deaths

Treatment-emergent AEs will be summarized by system organ class (SOC) and PT; by maximum relationship to study treatment (i.e., study drug related, study injection procedure related) as assessed by the investigator (e.g., reasonable possibility or no reasonable possibility) and SOC and PT; by maximum severity and SOC and PT; and by subject number and SOC and PT. Specific treatment-emergent AEs will be counted once for each subject for calculating percentages, unless stated otherwise. In addition, if the same AE occurs multiple times within a subject, the AE will be counted only once, and the highest severity and level of relationship to investigational product will be reported.

Serious AEs (including deaths) and AEs leading to study drug discontinuation will be summarized by SOC and PT and in listing format.

Possible distant spread of toxin PTs will be identified in the SAP and PDSOT TEAEs will be summarized by PT.

Neurological assessment TEAEs will be summarized by PT.

Vital sign measurements and 12-lead ECG parameters will be summarized for each assessment timepoint, as well as for changes from baseline at each assessment timepoint. In addition, potentially clinically significant vital signs values will be summarized. Details will be provided in the SAP.

Immunogenicity results, manifested as the presence of binding antibodies (positive) and neutralizing antibodies (positive) to AGN-151586, will be summarized in a table for baseline and postbaseline data. Immunogenicity findings (positive) will be tabulated with the number and percentage of subjects at each visit. Percentages will be based on the number of treated subjects with interpretable antibody assays at the specified visit. Immunogenicity results including additional analysis of antibody response to other neurotoxin serotypes will be documented in the CSR or in a separate report.

7.6 Overall Type I Error Control

For the double-blind period, to control the family-wise Type I error rate at 0.05 for multiplicity across the primary and secondary analyses, a hierarchical testing strategy will be used. The hierarchical testing strategy starts with the coprimary endpoint followed by sequential testing of the secondary endpoints. The statistical significance will be evaluated in the following order: if a statistical significance at the 0.05 level (2-sided) is shown for the first endpoint in the ranking order, then the next endpoint in the immediate subsequent order will be evaluated; evaluation of subsequent endpoint will continue in the same manner. If no statistical significance is shown at $\alpha = 0.05$ at any endpoint, then the endpoint and all subsequent endpoints will not be considered statistically significant, regardless of their nominal p-values.

The hierarchical testing order follows for US FDA:

- 1. Primary: At least a 2-grade improvement from baseline based on the following:
 - **Investigator and subject assessments** (composite) of GL severity at maximum frown at Day 7.
- 2. Secondary: *Mostly satisfied* or *Very satisfied* on the FLSQ follow-up version Item 5 (overall satisfaction) for GL at Day 7

- 3. Secondary: *Mostly satisfied* or *Very satisfied* on the FLSQ follow-up version Item 5 (overall satisfaction) for GL at Hour 24
- 4. Secondary: *Mostly satisfied* or *Very satisfied* on the FLSQ follow-up version Item 4 (natural look) for GL at Day 7

For the US FDA, the following secondary endpoints will be evaluated outside of the gated hierarchical testing sequence at each time point:

- 1. Key Secondary: At least 2-grade improvement from baseline in GL severity at maximum frown according to the **investigator assessment** using the FWS over time (double-blind period)
- 2. Key Secondary: At least 2-grade improvement from baseline in GL severity at maximum frown according to the **subject assessment** using the FWS over time (double-blind period).

The hierarchical testing order follows for EU regulatory agencies:

[figure not shown]
- 1. Coprimary: At least a 2-grade improvement based on the following:
 - Subject assessment using FWS at maximum frown at Day 7, and
 - Investigator assessment using FWS at maximum frown at Day 7.
- 2. Key Secondary: At least 20-point improvement from baseline in FLO-11 total scores for GL at Day 7
- 3. Secondary: At least 2-grade improvement from baseline in GL severity at maximum frown according to the **subject assessment** using the FWS at Hour 24
- 4. Secondary: At least 2-grade improvement from baseline in GL severity at maximum frown according to the **investigator assessment** using the FWS at Hour 24
- 5. Secondary: At least 1-grade improvement from baseline in GL severity at maximum frown according to the **subject assessment** using the FWS at Hour 24
- 6. Secondary: At least 1-grade improvement from baseline in GL severity at maximum frown according to the **investigator assessment** using the FWS at Hour 24
- 7. Secondary: *Mostly satisfied* or *Very satisfied* on the FLSQ follow-up version Item 5 (overall satisfaction) for GL at Hour 24
- 8. Secondary: *Mostly satisfied* or *Very satisfied* on the FLSQ follow-up version Item 4 (natural look) for GL at Day 7
- 9. Secondary: *Mostly satisfied* or *Very satisfied* on the FLSQ follow-up version Item 5 (overall satisfaction) over time
- 10. Secondary: At least 4-point improvement from baseline in FLO-11 Item 10 (look angry) for GL at Day 7
- 11. Secondary: At least 4-point improvement from baseline in FLO-11 Item 5 (look less attractive) for GL at Day 7

For the EU, the following secondary endpoints will be evaluated outside of the gated hierarchical testing sequence:

- 1. Secondary: Time to the first ≥ 1-grade improvement from baseline on the FWS according to subject assessments of GL severity at maximum frown (double-blind period)
- 2. Secondary: Time to the first ≥ 1-grade improvement from baseline on the FWS according to investigator assessments of GL severity at maximum frown (double-blind period).
- 3. Secondary: At least 2-grade improvement from baseline on the FWS according to subject assessments of GL severity at maximum frown over time (double-blind period)
- 4. Secondary: At least 2-grade improvement from baseline on the FWS according to investigator assessments of GL severity at maximum frown over time (double-blind period)
- 5. Secondary: Time to return to baseline FWS according to subject assessments of FWS at maximum frown (double-blind period)
- 6. Secondary: Time to return to baseline FWS according to investigator assessments of FWS at maximum frown (double-blind period)
- 7. Secondary: Subject-reported global assessment of change in GL based on the GAC-GL over time

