Hypothetical estimand for secondary categorical endpoints (US FDA; EU)	 Mostly satisfied or Very satisfied on the FLSQ follow-up version Item 5 (overall satisfaction) for GL at Hour 24 Mostly satisfied or Very satisfied on the FLSQ follow-up version Item 4 (natural look) for GL at Day 7 	Subjects who discontinue study prior to Hour 24 or Day 7 respective assessments for the FLSQ follow-up assessments will be included in the analysis as a hypothetical scenario in which the assessments were conducted as per protocol	Response rates and rate differences between AGN-151586 and placebo treatment groups; CMH test Gated hierarchical testing will be conducted.
Hypothetical estimand for secondary categorical endpoints (EU)	Mostly satisfied or Very satisfied on the FLSQ follow-up version Item 5 (overall satisfaction) for GL over time*	Subjects who discontinue study or who do not have FLSQ follow-up version Item 5 will be included in the analysis as a hypothetical scenario in which the assessments were conducted as per protocol	Response rates and rate differences between AGN-151586 and placebo treatment groups at each time point; CMH test Endpoints will be evaluated outside of the gated hierarchical testing.
Hypothetical estimand for secondary categorical endpoints (EU only)	 Key: Achievement of at least a 20-point improvement from baseline in FLO-11 total scores for GL at Day 7 Achievement of at least a 4-point improvement from baseline in FLO-11 Item 10 (look angry) for GL at Day 7 Achievement of at least a 4-point improvement from baseline in FLO-11 Item 5 (look less attractive) for GL at Day 7 	Subjects who discontinue study prior to Day 7 assessments or who do not have FLO-11 Day 7 assessments will be included in the analysis as a hypothetical scenario in which the assessments were conducted as per protocol	Response rates and rate differences between AGN-151586 and placebo treatment groups; CMH test . Gated hierarchical testing will be conducted.

	Attributes of the Estimand		
Estimand Label	Variables (Endpoints)	Handling of Intercurrent Events	Statistical Summary

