- I. Time to return to baseline FWS according to **subject assessment** of FWS at maximum frown (double-blind period)*
- m. Time to return to baseline FWS according to **investigator** assessment of FWS at maximum frown (double-blind period)*
- n. Mostly satisfied or Very satisfied on the FLSQ follow-up version Item 5 (overall satisfaction) for GL over time*
- o. ≥ 4-point improvement from baseline in FLO-11 Item 10 (look angry) for GL at Day 7
- p. ≥ 4-point improvement from baseline in FLO-11 Item 5 (look less attractive) for GL at Day 7
- q. Subject-reported global assessment of change in GL based on the Global Assessment of Change in Glabellar Lines (GAC-GL) over time*

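### Protocol 7.6 puts FLSQ Item 5 over time at step 9 of the EU testing order, although the protocol elsewhere and the SAP exclude it, so the status of two FLO-11 item endpoints depends on which document is followed

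*Protocol*

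**What the plan says.** Protocol 7.6 uses a fixed testing order in the double-blind period "to control the family-wise Type I error rate at 0.05 for multiplicity across the primary and secondary analyses". The second endpoint is evaluated only "if a statistical significance at the 0.05 level (2-sided) is shown for the first endpoint in the ranking order", and so on down the list. When an endpoint fails, "then the endpoint and all subsequent endpoints will not be considered statistically significant, regardless of their nominal p-values".

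The EU order in that section has 11 steps. Step 9 is response "on the FLSQ follow-up version Item 5 (overall satisfaction) over time". Step 10 is "At least 4-point improvement from baseline in FLO-11 Item 10 (look angry) for GL at Day 7" and step 11 is "At least 4-point improvement from baseline in FLO-11 Item 5 (look less attractive) for GL at Day 7". The section's seven-item list of EU endpoints outside the order does not contain the step 9 endpoint.

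Protocol 3.3 lists the same endpoint as EU item n, "Mostly satisfied or Very satisfied on the FLSQ follow-up version Item 5 (overall satisfaction) for GL over time", with an asterisk that takes it out of the hierarchy. The synopsis marks it the same way. Protocol Table 2 plans a CMH comparison for it at each time point and adds: "Endpoints will be evaluated outside of the gated hierarchical testing". SAP 3.2, SAP Table 2 and SAP 13.0 all exclude it.

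**The concern.** A fixed sequence works only if each step has one clear pass-or-fail decision and there is one agreed order. Here one section of the protocol makes two endpoints conditional on a third that the rest of the protocol, and the whole SAP, treat as unconditional and outside the order. That third endpoint produces one p-value per visit, and no rule reduces them to a single decision.

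At stake is whether the two FLO-11 item endpoints, look angry and look less attractive, can be declared significant in the EU. If overall satisfaction fails to separate from placebo at some visit, a reader of Protocol 7.6 could say that both are blocked. A reader of SAP 13.0 would say that they were properly tested after step 8.

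**Working it through.** **1. The passages side by side.**

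| Location | FLSQ Item 5 over time |
|---|---|
| Protocol synopsis, EU item n | excluded (asterisk) |
| Protocol 3.3, EU item n | excluded (asterisk) |
| Protocol 3.1, Table 2 | excluded; analysed at each time point |
| Protocol 7.6, EU order | **included, step 9 of 11** |
| SAP 3.2 | excluded (asterisk) |
| SAP Table 2 | excluded |
| SAP 13.0 | excluded; item 7 of the eight outside the order |

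Three of the four protocol locations and all three SAP locations agree. Removing the step leaves 11 − 1 = 10 steps, which is the SAP 13.0 order, with FLO-11 Items 10 and 5 at steps 9 and 10.

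**2. The plan's stated error rate.** The stated familywise rate is 0.05, two-sided. In a fixed sequence with one 0.05 decision per step, a false claim requires the first true null in the order to be rejected, which has probability at most 0.05. The coprimary step needs both tests to succeed, so it also stays at or below 0.05. The 10-step SAP order therefore meets the stated rate.

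**3. The missing rule.** In Protocol 7.6 every EU step except step 9 names a single time point (Day 7 or Hour 24), and the two-test coprimary step has a stated rule (Protocol 7.4). Step 9 has *k* p-values and no rule. *k* is unknown because the activity schedule is not in the text available.

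**4. Every-visit reading.** Let π be the power at each visit. For positively related visits, the chance of passing step 9, taken on its own, lies between π^k (independent visits) and π (perfectly correlated visits). Both π and *k* are assumptions.

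| π | k = 3 | k = 5 | k = 8 | upper limit |
|---|---|---|---|---|
| 0.99 | 0.970 | 0.951 | 0.923 | 0.99 |
| 0.90 | 0.729 | 0.590 | 0.430 | 0.90 |
| 0.80 | 0.512 | 0.328 | 0.168 | 0.80 |

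A visit with no true effect is significant with probability 0.05, so a single such visit caps the pass probability at 0.05. This reading is conservative: it costs power for the two FLO-11 items and does not raise the error rate.

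**5. Any-visit reading.** EU step 7 is the same item at Hour 24. If the over-time endpoint includes Hour 24 (an inference, since the schedule is not shown), step 9 is reached only when Hour 24 is already significant, and it then passes with probability 1. The FLO-11 items in effect follow step 8, as in the SAP. If the item has no effect at any visit, step 7 is itself a true null and step 9 is reached at most 5% of the time.

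**6. Result.** The readings lead to different routes to the last two endpoints. Nothing earlier in the EU order changes, and the US order does not contain the step.

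**The case against.** The best defence is that the SAP governs and is clean. Protocol 7.1 leaves full analysis detail to the SAP, and SAP 1.0 says that it changes some protocol analyses and points to Section 14.0. The SAP under review is version 5.0 of 08 April 2023, later than the protocol synopsis of 01 August 2022, and it excludes the endpoint everywhere. Step 9 looks like a leftover line. Most of this stands: an analysis run under SAP 13.0 never meets the step.

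What it leaves open is the record. The visible part of SAP 14.0 has only a general version 2.0 entry (15 February 2022) about included and excluded endpoints in the testing sequences. It does not name this endpoint or Protocol 7.6. Some entries are redacted, so this concerns only what can be seen. No visible text says which document prevails on the testing order.

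A reader might infer two stronger points that the documents do not support:

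- **Familywise error is inflated.** An any-visit rule applied to five independent null visits would give 1 − 0.95^5 = 0.226. That treats step 9 as a free-standing test and ignores step 7. It also requires a pass rule and a set of visits that the plan does not state.
- **The protocol knowingly restored the step after the SAP removed it.** This compares the August 2022 protocol only with SAP version 2.0. The current SAP is later than the protocol, the version 2.0 entry does not name the endpoint, and version 3.0 (15 November 2022) also revised secondary endpoints. The documents do not show when the endpoint left the hierarchy.

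**Conclusion.** Wrong as written, and a minor to moderate protocol–SAP reconciliation. Protocol 7.6 contradicts three other places in the protocol and three in the SAP, and its step 9 has no pass rule. The consequence is limited to whether the two last-ranked EU secondary endpoints can be declared significant. The coprimaries, the key secondary, EU steps 3 to 8 and the US sequence stand as they are.

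The textual conflict rests on no assumption. The possible loss under an every-visit reading depends on assumed visit counts and per-visit power, so those figures are illustrations only. The argument that an any-visit reading is harmless assumes that Hour 24 is one of the visits.

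**What to change.** In Protocol 7.6, move step 9 to the EU list of endpoints outside the hierarchy, and renumber FLO-11 Items 10 and 5 as steps 9 and 10, matching SAP 13.0. In SAP 14.0, name this change and state that the SAP 13.0 order governs. Give the date of that decision relative to unblinding only if it can be verified, because the documents show no unblinding or database-lock date.

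If the sponsor did intend the endpoint to be in the order, the alternative is to name one time point or a combination rule and to align the synopsis, Protocol 3.3, both versions of Table 2, SAP 3.2 and SAP 13.0.

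The preferred change costs one line in a protocol amendment or clarification and one line in the SAP version history. It needs no new data and no change to the sample size.

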7.7 Sample Size Determination

For the FDA and EU regulatory agencies, a gate-keeping testing strategy will be used to compare the AGN-151586 group versus the placebo group, starting with the primary endpoint(s) and sequentially testing in the endpoint hierarchy at the 0.05 significance level.

8 ETHICS

8.1 Independent Ethics Committee/Institutional Review Board (IEC/IRB)

The protocol, informed consent form(s), recruitment materials, and all subject materials will be submitted to the IEC/IRB for review and approval. Approval of both the protocol and the informed consent form(s) must be obtained before any subject is enrolled. Any amendment to the protocol will require review and approval by the IEC/IRB before the changes are implemented to the study. In addition, all changes to the consent form(s) will be IEC/IRB approved.

8.2 Ethical Conduct of the Study

The study will be conducted in accordance with the protocol, Operations Manual, International Council for Harmonisation of Technical Requirements for Pharmaceuticals for Human Use (ICH) guidelines, applicable regulations, and guidelines governing clinical study conduct and the ethical principles that have their origin in the Declaration of Helsinki. Responsibilities of the investigator are specified in Appendix B. Investigators should notify AbbVie if any urgent safety measures are taken to protect the subjects against any immediate hazard.

8.3 Subject Confidentiality

To protect subjects' confidentiality, all subjects and their associated samples will be assigned numerical study identifiers or "codes." No identifiable information will be provided to AbbVie.

9 SOURCE DOCUMENTS AND CASE REPORT FORM COMPLETION

The investigator is responsible for ensuring the accuracy, completeness, legibility, and timeliness of the data reported. All source documents should be attributable, legible, contemporaneous, original, accurate, and complete to ensure accurate interpretation of data. Clinical site monitoring is conducted to ensure that the rights and well-being of human subjects are protected, that the reported trial data are accurate, complete, and verifiable, and that the conduct of the trial is in compliance with the currently approved protocol, ICH Good Clinical Practice (GCP), and applicable local regulatory requirement(s). During the COVID-19 pandemic, remote data review/verification may be employed if allowed by the local regulatory authority, IRB/IEC, and the study site.

10 DATA QUALITY ASSURANCE

AbbVie will ensure that the clinical trial is conducted with a quality management system that will define quality tolerance limits in order to ensure human subject protection and reliability of study results. Data will be generated, documented, and reported in compliance with the protocol, ICH GCP, and applicable regulatory requirements.

11 COMPLETION OF THE STUDY

The start-of-study is defined as the date of the first site activated.

The end of study is defined as the date of end of study participation by the last subject in the last country where the study was conducted.

APPENDIX A. STUDY-SPECIFIC ABBREVIATIONS AND TERMS

Abbreviation	Definition
--------------	------------

ADR adverse drug reaction

AE adverse event

BoNT/A Botulinum Neurotoxin Serotype A

COVID-19 Cochran-Mantel-Haenszel
COVID-19 Coronavirus Disease – 2019

CSR clinical study report

DHEA Dehydroepiandrosterone

ECG Electrocardiogram

eCRF electronic case report form

EDC electronic data capture

EU European Union

FDA Food and Drug Administration
FLO-11 11-item Facial Line Outcomes

FLSQ Facial Line Satisfaction Questionnaire

FWS Facial Wrinkle Scale

GAC-GL Global Assessment of Change in Glabellar Lines

GCP good clinical practice

GL Glabellar lines

HRT hormone replacement therapy

ICH International Council for Harmonisation of Technical Requirements for Pharmaceuticals

for Human Use

IEC independent ethics committee

IMP investigational medicinal product

IRB institutional review board

IRT interactive response technology

ITT intent-to-treat

IUD intrauterine device

MedDRA Medical Dictionary for Regulatory Activities

NRI non-responder imputation

STUDY M21-500 | Version 2.0 | EudraCT 2021-003667-10 CONFIDENTIAL INFORMATION

Abbreviation Definition

PDSOT possible distant spread of toxin

PRO patient reported outcome

PTs preferred terms

SAE serious adverse event
SAP statistical analysis plan
SAR serious adverse reaction

SARS-CoV-2 severe acute respiratory syndrome coronavirus 2

SOC system organ class

SUSAR suspected unexpected serious adverse reactions

TEAE treatment-emergent adverse event
WOCBP Women of childbearing potential

APPENDIX D. ACTIVITY SCHEDULE

APPENDIX E. PROTOCOL SUMMARY OF CHANGES

Previous Protocol Versions

Protocol	Date
Version 1.0	10 November 2021
Version 1.1 (Germany Only)	19 July 2022

The purpose of this version is to correct minor clerical errors for consistency throughout the protocol in addition to the following:
